Aim 1: To evaluate clinical effectiveness of the Pre-NDPP intervention. We will recruit 500 diverse, predominately low-income patients with elevated diabetes risks (e.g., prediabetes) in the Denver Health safety net healthcare system. We will conduct a RCT to compare NDPP attendance and weight loss outcomes between participants randomized to receive the Pre-NDPP enhancement vs. direct enrollment into the NDPP (usual care). Pre-sessions, led by trained Lifestyle Coaches, will focus on providing information on diabetes risks and locally available resources to reduce risk, including the NDPP. Coaches will use MI techniques to help participants identify an actionable plan to reduce risk, such as attending NDPP sessions, and guide participants in identifying barriers and possible solutions that would enable participation. Pre-NDPP participants and usual care NDPP participants will be assigned to separate NDPP classes to prevent contamination of Pre-NDPP effects. We will collect data on demographics, NDPP outcomes (primary outcome is percent weight loss), potential mediators, implementation factors, and cost. We hypothesize that Pre-NDPP participants will have greater engagement and weight loss compared to those who are directly enrolled into the program (usual care).

Aim 2: To examine mediators and moderators of Pre-NDPP outcomes. We will explore potential mediators (perceived risk for developing diabetes and self-efficacy and readiness for weight control) and key sociodemographic variables (race/ethnicity and income level) as potential moderators of intervention effectiveness that are important to understand for future uptake by stakeholders. We hypothesize that a) Pre-NDPP will increase perceived risk, self-efficacy, and readiness, which will mediate relationships between presession treatment and NDPP outcomes, and that b) race/ethnicity and income level will moderate Pre-NDPP effectiveness.

Aim 3: To evaluate the implementation factors of Pre-NDPP. In preparation for potential future dissemination, we will evaluate implementation factors following a RE-AIM framework⁸, including a qualitative evaluation of pre-sessions from a Lifestyle Coach, clinic provider/personnel, and patient perspective. We will

also evaluate the cost of adding pre-sessions to NDPP delivery and projected return on investment (ROI). We hypothesize that Pre-NDPP will be implementable and yield sufficient projected ROI to justify its cost.

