We will assess potential mediators of perceived risk and self-efficacy, key constructs of the Health Belief Model, ²⁶ as well as readiness for weight loss as an indicator of motivation. Perceived risk for developing diabetes will be assessed with the Risk Perception Survey for Developing Diabetes, a 53-item Likert scale measure with four subscale scores on Comparative Disease Risk, Environmental Risk, Personal Control, and Optimistic Bias. ^{41,42} Self-efficacy for weight control will be measured with the Weight Efficacy Lifestyle Questionnaire, a 20-item measure of confidence (on a 10-point scale) managing five situational factors related to weight management behavior: negative emotions, availability, social pressure, physical discomfort, and positive activities. ⁴³ We will use validated Spanish-language versions of both measures. ^{42,44} Weight loss readiness will be assessed with the Stages of Change in Overweight and Obese People (S-Weight), a 5-item survey developed concurrently in English and Spanish by expert consensus. ^{45,46} Mediators will be measured during an initial assessment at the time of enrollment and 1-2 weeks prior to the first NDPP session (i.e., about one week after pre-sessions are completed for the Pre-NDPP arm, and shortly before NDPP classes begin for both arms). This will determine whether Pre-NDPP results in increased perceived risk, self-efficacy, and readiness compared to the usual care NDPP, and whether changes in these variables mediate outcomes.

Data collection for Aim 3. RE-AIM is a planning and evaluation framework for implementation research that will guide our evaluation of Pre-NDPP delivery and effectiveness.⁸ RE-AIM constructs will be assessed through a combination of recruitment data, intervention outcomes, staff logs, observations, and interviews with Lifestyle Coaches, clinic personnel, and patients, as well as cost records (Table 1). [name] holds expertise in implementation research and will lead qualitative data collection with [name] (Qualitative Research Assistant; QRA), first developing semi-structured interview guides⁴⁷, surveys, and a structured observation template. Health economist [name] will lead cost-related data collection.

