| Risk perception | Risk Perception Survey for Developing Diabetes ⁴² | Administered by Lifestyle Coaches during first study visit | BL and 1-2 weeks prior | | | |
| Self-efficacy | Weight Efficacy Lifestyle Questionnaire ⁴³ | and repeated prior to start of NDPP classes to assess pre- | to start of NDPP | | | |
| Readiness | Stages of Change in Overweight and Obese People ^{45,46} | post change | classes | | | |
| | Implementation factors | | | | | |
| Reach – Absolute number, proportion, and representativeness of individuals who participate | # and characteristics of patients referred, outreached, and express interest, consent, complete Pre-NDPP (intervention group), and attend NDPP (both groups); Reasons for not enrolling or dropout | Demographics and referral data from EHR; enrollment and participation data collected by coaches; reasons for participating or declining collected by QRA interviews with select participants | Ongoing collection | | | |
| Effectiveness- Intervention impact on key outcomes | Based on main outcomes listed above | | | | | |
| Adoption – Absolute number, proportion, and representativeness of settings and agents willing to initiate intervention | # and characteristics of participating DH clinics; NDPP referrals; Lifestyle Coach participation | Study documentation; EHR data | Monthly abstraction analysis | | | |
| | Factors influencing adoption | QRA interviews with Lifestyle Coaches and select clinic personnel | BL (for coaches and clinic personnel); 6 months after start of Pre-NDPP (for coaches | | | |

| | | | only) |
|---|--|---|---|
| Implementation – Fidelity to intervention protocol, including | Completion of Pre-NDPP and NDPP protocol components | Coach documentation; Presession shadowing by QRA; Fidelity checks | Ongoing collection |
| consistency of delivery (e.g., bias) and time and cost of intervention | Acceptability of Pre-NDPP components, processes and tools; any adaptations made by coaches | Interivew by QRA with Lifestyle Coaches | 6 months after start of Pre-NDPP |
| | Process, barriers, facilitators to implementing Pre-NDPP | QRA interviews with select participants, select clinic personnel and Lifestyle Coaches | 12 months after start of Pre-NDPP (for clinic personnel and coaches); 1- 2 months after last intervention session attended (for participants) |
| | Pre-NDPP cost | Lifestyle Coach time and resources survey | Quarterly after each pre-session |

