Description of the Pre-NDPP protocol. The Pre-NDPP protocol was previously developed in a pilot study funded by the Colorado Department of Public Health and Environment. The protocol is based on the Health Belief Model²⁶ and extensive stakeholder engagement, including feedback from previous NDPP participants and Lifestyle Coaches. Pre-sessions are intended to increase motivation and readiness to engage in the NDPP, while helping participants become comfortable with the group class format. Content was developed for a 4th grade reading level. Pre-sessions focus on 1) education on diabetes risks, 2) MI to participate in the NDPP, and 3) problem-solving of barriers to engagement. Pre-sessions are scheduled for 1 hour to minimize burden, but are flexible in practice, lasting 60-90 minutes to address individual questions and needs. Pre-sessions will be held 1-2 weeks before NDPP classes start, at the same day, time, and location to facilitate transitions to the NDPP. We will hold pre-sessions remotely when needed per COVID-19 restrictions on inperson meetings. To minimize bias, Lifestyle Coaches will be assigned each quarter to deliver one Pre-NDPP and one usual care NDPP classes, with accompanying fidelity observations. Moreover, there have been no significant differences in NDPP outcomes among coaches (e.g., 1.5% vs. 1.6% mean weight loss among participants attending ≥1 session with [name] and [name], respectively, p=.475). The research coordinator is also a trained Lifestyle Coach and will assist in all pre-sessions.

Pre-NDPP participants will first receive education on diabetes risks and information about available resources to reduce risk, including a description of the NDPP. Education is informed by the Health Belief Model²⁶ in which perceived risk, severity, benefits of and barriers to action, and cues to action determine health behavior. Topics include: a) an overview of T2D (e.g., prevalence, common complications) and risks for developing T2D (e.g., prediabetes, sedentary lifestyle, overweight/obesity), b) rates of T2D onset, c) guidance that modest weight loss can reduce risk, and d) evidence-based resources to prevent T2D, including a detailed overview of the NDPP. Guidance is intended to normalize the experience of being at-risk for T2D to reduce anxiety, while focusing on instilling hope that T2D is preventable and making calls to action.

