Coaches will then use MI techniques (e.g., reflective listening, evoking ambivalence, rolling with resistance, and eliciting change talk)²⁹ to help participants identify their preferred plan of action to reduce risk, encouraging participation in NDPP sessions. For example, to create discrepancy, coaches will acknowledge the difficulty of making changes in health behavior and probe for typical experiences of weight loss followed by weight regain or other similar challenges. To counter-balance these challenges, coaches will encourage participants to describe why preventing T2D is important to them (e.g., wanting to live a long and healthful life or setting a positive example for their children and grandchildren). Coaches will also non-judgmentally acknowledge that while the NDPP works well for those who attend regularly, it may be challenging for some individuals to attend a yearlong class, and that it is okay to opt out or choose other risk reduction resources.

Finally, to plan behavior to reduce diabetes risk, participants will be guided toward developing a personalized SMART (Specific, Measurable, Achievable, Realistic, and Time-bound) strategy for attending the NDPP. Coaches will help participants identify their anticipated barriers to attendance (e.g., need for childcare) and possible solutions that would enable participation (e.g., finding other caregivers or bringing children to class on occasion if needed). Participants will also be encouraged that more frequent attendance is associated with greater weight loss, but overall benefits can be achieved despite missing some sessions: attending ≥15 sessions is associated with achieving the ≥5% weight loss goal on average (i.e., each session is associated with 0.31% weight loss⁴). Scaling questions will be used to help individuals identify an appropriate initial goal. For example, although some participants may have limited confidence to make a commitment to attend the yearlong NDPP without having tried it before, they may report a 10 of 10 in confidence to attend at least the first NDPP session. Lastly, participants will complete an individualized action plan that includes their SMART goal and anticipated problem-solving strategies.

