D. Description, Risks, and Justification of Procedures and Data Collection Tools.

- 1) Pre-NDPP and NDPP classes
 - a. Description (see above description in section C)
 - b. Risks: Discussing diabetes risks may also be emotionally stressful. Muscle soreness or minor injury may occur from engaging in physical activity as recommended in the NDPP. To be safe, we encourage starting slowly with physical activity and checking with a doctor as needed. Participants may experience anxiety or distress related to answering personal questions or having weight collected. The National Diabetes Prevention Program classes are held in groups of other participants. We will ask the class to not share sensitive personal information outside of the group, but privacy cannot be guaranteed.
 - a. Why necessary: The one-time Pre-NDPP classes are being studied to see if they increase engagement in NDPP classes.
- 2) Study visits for survey completion and weight assessment
 - a. Description: Study visits will occur for 1) an initial eligibility and baseline assessment held in person (or remotely when needed due to restrictions on in-person meetings), 2) a follow up assessment in person, electronically, by mail, or by phone 1-2 weeks prior to the start of NDPP classes, and 3) a 12-month weight assessment in person (or collected remotely when needed).
 - b. Risks: Participants may experience anxiety or distress related to answering personal questions or having weight collected. The study investigators will make every effort to keep records private but it cannot be guaranteed.
 - c. Why necessary: Quantitative data collected from these visits will be used to answer research questions about the effectiveness of Pre-NDPP.

3) Interviews

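### Lifestyle Coaches, who also lead the pre-session, give the perceived-risk, self-efficacy and readiness scales about a week after it, so any extra wish to please them would be read as a Pre-NDPP effect on the mediators

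*Combined protocol and SAP*

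**What the plan says.** Table 1 (section IV.A, Mediators) gives one collection method for the risk perception, self-efficacy and readiness scales. They are "Administered by Lifestyle Coaches during first study visit", "and repeated prior to start of NDPP classes to assess pre"-to-post change. No other administrator is named.

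Aim 1 has "Pre-sessions, led by trained Lifestyle Coaches". The description of the Pre-NDPP protocol in section IV.C states the purpose: "Pre-sessions are intended to increase motivation and readiness to engage in the NDPP". The session also teaches diabetes risk and uses motivational interviewing. Section IV.A places the repeat assessment "about one week after pre-sessions are completed for the Pre-NDPP arm"; the usual care arm has no such session.

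Two safeguards against bias are described in section IV.C. One is that "Lifestyle Coaches will be assigned each quarter to deliver one Pre-NDPP and one usual care NDPP classes, with accompanying fidelity observations". The other is observation of NDPP classes for fidelity and for bias in their delivery. Neither mentions the questionnaires.

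Section IV.D, item 2, allows "a follow up assessment in person, electronically, by mail, or by phone 1-2 weeks prior to the start of NDPP classes". It does not say which mode is the default, who gives the scales when help is needed, or whether the mode is to be recorded.

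**The concern.** The mediators are self-reports from unblinded participants, collected by the staff role that delivers the intervention. By the second administration, Pre-NDPP participants have just been coached on diabetes risk, motivation and readiness. Usual care participants have not. If the session makes people more inclined to tell a coach that they feel at risk, confident or ready, the scores move without any change in the construct.

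Hypothesis 2.1 is tested by the arm-by-time coefficient alone, and Hypothesis 2.2 uses change in the same scores as its main independent variables. Section II says that uptake by providers and payers is expected to depend on understanding how Pre-NDPP achieves its effect. A reporting artefact would therefore damage evidence for which the plan has a stated use. It cannot be removed once the data are in, particularly if mode and administrator were not recorded.

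**Working it through.** **1. The documents side by side.** The same role gives the scales at both times (Table 1) and leads the pre-session (Aim 1; section IV.C). Only one arm has the pre-session, about a week before the repeat (section IV.A). The stated bias checks concern class delivery. The recruitment steps in section IV.C also list randomization before the initial assessment, so coaches could know the allocation at baseline too.

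**2. Hypothesis 2.1.** The coefficient tested is the difference between arms in mean change. Suppose the true difference is θ and reports in the Pre-NDPP arm shift by a further δ at follow-up. The model then estimates θ + δ, and nothing in it separates the two.

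**3. Hypothesis 2.2.** Let outcome Y = c′A + bM + error, where A is arm and M is true mediator change. If observed change is M* = M + δA, then Y = (c′ − bδ)A + bM* + error. The arm-to-mediator path rises by δ, the apparent indirect effect rises by bδ, and the direct effect falls by bδ. The slope b is unchanged. This assumes that arm stays in the model, as it does in the Hypothesis 1.1 approach to which the plan refers.

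**4. Size.** The plan gives no SD, ICC or power for the mediators, so there is no stated mediator figure to reproduce. The only sample-size basis is Table 2, which concerns percent weight loss. Its rows for 10 groups of 20 per arm reproduce with effective n = 200 / (1 + 19 × ICC):

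- ICC 1%: 200 / 1.19 = 168.1 (stated 168)
- ICC 2%: 200 / 1.38 = 144.9 (stated 145)

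Borrowing these, the standard error of the difference in mean change, in SDs of change, is √(2/n): √(2/145) = 0.117 and √(2/168) = 0.109. With a true effect of zero, the two-sided rejection probability at α = .05 is 1 − Φ(1.96 − δ/SE) + Φ(−1.96 − δ/SE). For example, δ = 0.2 and n = 145 give δ/SE = 1.70, and the probability is 0.399.

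| Assumed shift δ (SD of change) | All follow-up forms coach-given, n = 145 to 168 | Half coach-given (average shift δ/2) |
|---|---|---|
| 0 | 5% | 5% |
| 0.1 | 14–15% | 7% |
| 0.2 | 40–45% | 14–15% |
| 0.3 | 72–79% | 25–28% |

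The shifts, the half-and-half split and the use of the weight ICC for questionnaire scores are all assumptions.

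**The case against.** Several stronger readings are tempting, and the documents do not support them.

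- **Pressure to please exists in one arm only.** It does not. Coaches phone, screen and survey participants in both arms, and each coach is assigned a class in each arm. Only an increment after the pre-session can differ. Even its direction is not certain: the session tells participants that opting out is acceptable and tries to normalise being at risk.
- **The participant's own pre-session coach gives the survey.** The plan does not say this. Section IV.A speaks of both Lifestyle Coaches, so with a team that small it is plausible, but it is not stated.
- **The pre-session rehearses the self-efficacy scale.** In section IV.C the example is that "they may report a 10 of 10 in confidence to attend at least the first NDPP session". That is confidence to attend a class. The scale asks about weight control under negative emotions, availability, social pressure, physical discomfort and positive activities. The rating format is similar, but the construct is not.
- **The false-positive rates are 17%, 52% and 85%.** These follow from 200 independent participants per arm and a baseline-to-follow-up correlation of 0.5, where SE = √(2 × 0.5 × 2/200) = 0.10. The Hypothesis 2.1 model has a group random effect, so clustering must be allowed for, and the correlation is not in the documents.
- **The shift weakens the link from mediator to outcome.** A uniform shift does not, as step 3 shows. Attenuation would need shifts that vary between people, and nothing in the documents speaks to that.

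It is also fair to say that electronic and mail completion are already allowed at follow-up, that coach administration is a common pragmatic choice, and that the plan calls mediation and moderation exploratory. These points limit the concern but do not answer it. No rule makes self-completion usual, Table 1 still names coaches, and the exploratory label does not clearly cover Hypothesis 2.1, which is an arm comparison under the general two-sided .05 rule.

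**Conclusion.** The point stands as a measurement weakness confined to Aim 2. As planned, the Hypothesis 2.1 test and the arm-to-mediator path in Hypothesis 2.2 cannot tell a reporting shift from a true change, and the stated safeguards do not reach questionnaire administration. Whether a shift would occur, and how large it would be, cannot be derived from the documents. The tabulated rates show sensitivity to an assumed bias; they do not predict one. They matter because even a shift of 0.1 SD of change would nearly triple the nominal error rate if every form were coach-given.

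The primary outcome, percent weight change, does not use these scales and is unaffected. The change is worth making because it is cheap, not because the trial's main conclusion is at risk.

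**What to change.** Reconcile Table 1 with section IV.D, item 2, and state one rule for the follow-up scales in both arms:

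- The scales are self-completed, electronically or by mail, where the participant is able.
- Otherwise they are given by the Lifestyle Coach who did not and will not lead that participant's pre-session or class. The research coordinator and the qualitative research assistant should not do this, because the first assists in all pre-sessions and the second shadows them.
- Modes are offered in the same way in both arms, so that the mode mix is the same and any effect of mode itself cancels in the arm-by-time term.
- Mode and administrator are recorded for every form, and a sensitivity analysis of Hypotheses 2.1 and 2.2 by mode is specified in section IV.F. Mode will depend partly on the participant, so this analysis is supportive only.

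No new staff are needed, and using the other coach keeps a bilingual administrator available. The cost is some scheduling between coaches and possibly slightly lower completion among those who self-complete. The battery has 53 + 20 + 5 = 78 items, and the pre-session materials were written for a 4th grade reading level, so self-completion should not be forced. The change lessens self-report bias but does not remove it, because participants still know which arm they are in.

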Data collection for Aims 1 and 2. This RCT focuses on comparing NDPP outcomes between participants who receive Pre-NDPP vs. direct enrollment into the NDPP. The assessment schedule is shown in Table 1 below. Demographic characteristics will be extracted from EHR databases and verified as needed during the first study visit, including age, gender, race/ethnicity, preferred language, income (above/below 133% of federal poverty level), and education (highest level completed). Body weight will be measured on a high-capacity medical-quality scale at study visits and NDPP sessions. We will also provide study participants with a commercial-grade scale for in-home use (e.g., Inevifit's Premium Bathroom Scale I-BS002; https://www.inevifit.com/product/inevifit-premium-bathroom-scale-w-led-display-silver/) so that they can send us a picture of their weight via text message or email when not meeting in-person. The primary outcome is percent weight change from baseline to 12-months by ITT analysis (without regard to whether participants declined NDPP or had early dropout). We will also calculate percent weight change from the first to last NDPP sessions attended (i.e., last observation carried forward), per CDC guidelines.³⁷ CMS standards for NDPP reimbursement also emphasize achieving ≥5% weight loss at any point in the program, ¹⁰ assessed as a

dichotomous outcome. Attendance in the NDPP will be measured as ≥1 session attended, total number of NDPP sessions attended (including make-up sessions), and duration of participation in the yearlong program. We will also record how many sessions were attended remotely vs. in-person. Rates of completing between-session support calls will also be assessed as an additional indicator of engagement and treatment dose. Per the CDC's NDPP curriculum, participants will self-report weekly minutes of moderate to vigorous physical activity since the last session.³ Baseline BMI will also be assessed at the initial study visit as kg/m². If the initial study visit is held remotely (i.e., due to restrictions to meeting in-person per COVID-19), we will collect BMI by confirming height from a participant's medical record, and mailing a scale to participants for them to send us a picture of their weight within 1-2 weeks.

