We will measure Pre-NDPP costs using principles of time-driven activity based costing, ^{48,49} accounting for Lifestyle Coach and supervisor time (including salaries and benefits), supplies and other direct costs, and indirect costs (e.g., facilities and general administrative expenses). To focus on Pre-NDPP, we will exclude other costs associated with standard NDPP delivery and research-related costs (e.g., data collection solely for research purposes). To facilitate accurate estimates of personnel costs, coaches and their supervisor will track time spent on Pre-NDPP activities (e.g., training, outreach, preparing for and conducting Pre-NDPP) and report total hours for each Pre-NDPP activity quarterly. Supplies and other direct costs will also be reported quarterly. Standard cost collection guides will be used by study staff.

| Measure | easure Description Method of Collection | | | | | |
|--|--|--|---|--|--|--|
| Characteristics | | | | | | |
| Demographics | Age, gender, race/ethnicity, primary language, income, education, household composition, etc | Collected from EHR and during first study visit | BL | | | |
| Body mass index | Baseline body mass index (kg/m²) | Collected during first study visit (or within 1-2 weeks of remotely-conducted initial study visits) | | | | |
| | Main outcom | les | T | | | |
| Initial NDPP attendance | ≥1 NDPP session attended 1-25 NDPP sessions attended | Collected during NDPP delivery; | | | | |
| # of sessions attended | (including virtual vs. in-person sessions) | Note weight is also measured at an initial study assessment and at a final 12-month study visit | | | | |
| Duration in NDPP | 1-365 days of NDPP participation | (we are setting up a time for all randomized individuals to have | | | | |
| # of between-session calls completed | 1-25 between-session support calls completed | their weight measured at these study visits, for which they will | Ongoing collection | | | |
| Physical activity | Average self-reported weekly minutes at each NDPP session | receive gift cards). Participants may also text/email a picture of | | | | |
| Percent weight change | Based on a) BL to 12 months (primary outcome), and b) first to last NDPP sessions attended | their weight using a study- provided scale for in-home use if not meeting in-person for weight | | | | |
| ≥5% weight loss | Achieved at any point in the NDPP | collection. | | | | |
| | Mediators | | T | | | |

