Recruitment. We will identify potential participants through referrals from healthcare providers at DH, which is known to support initial enrollment in the NDPP.²¹ Providers refer through the electronic health record (EHR) per usual practice. Since 2013 over 7,000 at-risk patients were referred by providers to the DH NDPP. If needed to meet recruitment goals, we will also identify participants from a risk registry based on EHR data, which has previously identified over 10,000 NDPP-eligible patients annually. The enrollment process after initial identification will be as follows: 1) Lifestyle Coaches pre-screen via medical record review and contact referrals by phone to verify interest, eligibility, and schedule eligible individuals for an initial screening visit (held in-person or remotely as needed), 2) consenting individuals are randomized to receive Pre-NDPP or usual care NDPP (note we will use Denver Health's e-consent process for any virtually-conducted recruitment visits), and 3) complete an initial assessment (behavioral and anthropometric assessments), 4) the Pre-NDPP group completes a pre-session 1-2 weeks before NDPP classes start, 5) both groups complete a follow up behavioral

assessment 1-2 weeks before NDPP classes start (collected in-person or remotely as needed), and 6) both groups commence yearlong NDPP classes (held in-person or remotely as needed).

We will initially enroll 500 participants, with a goal of 400 randomized participants across both groups attending ≥1 NDPP session as based on statistical power estimates (see Sample Size and Power Calculations below). From previous experience, we expect approximately 50% of referred patients to express interest in participating upon initial outreach. Then after initial assessment, we expect early attrition of approximately 20% of consenting participants. We will seek to recruit 50 individuals every 3 months, for a total of 500 participants recruited over 2.5 years (i.e., 200 participants annually). From 2013-2017, we recruited 300 NDPP participants on average each year. Thus, we expect to fully meet RCT recruitment goals. Demographic characteristics of individuals in this study are expected to approximately match characteristics of all previous NDPP participants at DH: 78.0% female, 58.2% Hispanic, 19.5% NHB, 21.0% NHW, 61.4% low-income (including a majority of low-income individuals within each racial/ethnic group), and a mean age of 48.4 (SD=12.7) years.

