Randomization. We will randomize eligible, consenting participants to receive either the enhanced intervention (Pre-NDPP + standard NDPP) or usual care control group (standard NDPP only) in a 1:1 ratio. After defining our randomization parameters, including allocation by varying block sizes and stratification by demographic characteristics, we will use the Randomization Module of the Research Electronic Data Capture system (REDCap) to manage random assignment of participants.

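### Randomisation is listed before the baseline assessment and nothing withholds allocation, so questionnaires and remote baseline weights can be collected after the arm is known

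*Combined protocol and SAP*

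**What the plan says.** The Recruitment paragraph of section IV.C sets out enrolment as a numbered sequence. Step 1 is record review and a phone call to check interest and eligibility. Step 2 reads "2) consenting individuals are randomized to receive Pre-NDPP or usual care NDPP". Step 3 continues "and 3) complete an initial assessment (behavioral and anthropometric assessments".

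Other sections touch on the same events without ordering them:

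- **Randomization (IV.C):** "We will randomize eligible, consenting participants to receive either the enhanced intervention", stratified by demographic characteristics and managed in REDCap.
- **Study visits (IV.D):** the first visit is "an initial eligibility and baseline assessment held in person (or remotely when needed due to restrictions on in-person meetings". Randomisation is not mentioned.
- **Outcome Measure(s) (IV.A):** "The primary outcome is percent weight change from baseline to 12-months by ITT analysis". If the first visit is remote, height comes from the medical record and weight is obtained by "mailing a scale to participants for them to send us a picture of their weight within 1-2 weeks".
- **Table 1 (IV.A):** BMI is collected at the first visit "or within 1-2 weeks of remotely-conducted initial study visits". The mediator questionnaires are administered by Lifestyle Coaches at the first visit. For weight, "we are setting up a time for all randomized individuals to have" it measured at the initial and 12-month assessments.

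**The concern.** Baseline data are safest when recorded before anyone knows the arm. Here the only stated order is the reverse, and no section describes masking or says when participants and coaches learn the assignment.

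Two kinds of baseline data are exposed. The first is the set of questionnaires on perceived risk, self-efficacy and readiness. They are self-reported and given by coaches who also deliver the classes. The second is the remote baseline weight, self-taken at home. Knowing the arm could affect whether it is sent, when, and what it shows. Because it is the reference value for percent change, any arm-related difference passes into the primary contrast. Loss before that weight is sent could also differ by arm, and a randomised person who never sends it has no observed primary outcome.

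**Working it through.** No planned figure is in dispute, so the check is mainly a comparison of text.

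**1. Is the order settled anywhere else?** Outcome Measure(s) places the mediator questionnaires at enrolment, Retention places the first paid assessment at initial recruitment, and Table 1 and section IV.D refer to the first visit. None of these says before or after randomisation. The numbered list in Recruitment is the only explicit order.

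**2. Does eligibility force a weight before assignment?** BMI is an eligibility criterion (IV.B), and only eligible people are randomised. But step 1 of Recruitment already verifies eligibility by record review and phone. No stated input to randomisation needs a study weight or a questionnaire.

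**3. Does a combined eligibility and baseline visit settle it?** For an in-person visit it largely removes the concern about weight, which is taken on a medical-quality scale at that visit. For a remote visit it does not. The scale is mailed and the photo may follow 1-2 weeks later, and no section holds the assignment until it arrives.

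**4. What happens if the baseline weight never comes?** General quantitative approaches (IV.F) includes everyone randomised in the ITT analysis. Retention promises imputation as appropriate and points to the Analysis Plan. The missing-data methods there are framed for longitudinal analyses, and no rule covers a missing baseline weight. Weights at class sessions exist for attenders, but no section names them as a substitute. In the Pre-NDPP arm they are taken after the pre-session.

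**5. How large could the effect be?** Let *f* be the share of first visits that are remote, and *d* the arm difference in mean baseline weight, in percent, caused by knowing the arm among those participants. The between-arm shift in recorded baseline is *f* × *d*. If recorded baseline is *b*% above the true value and true loss is *L*%, then

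recorded loss = 100 × [1 − (1 − *L*/100)/(1 + *b*/100)].

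Taking the pilot means as *L* (1.5% and 3.4%, Preliminary Studies) and assumed values of *b*:

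| *b* (assumed) | Added to recorded loss, *L* = 1.5 | Added to recorded loss, *L* = 3.4 |
|---|---|---|
| 0.25 | 0.246 points | 0.241 points |
| 0.5 | 0.490 points | 0.481 points |
| 1.0 | 0.975 points | 0.956 points |

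The contrast therefore moves almost one for one with *f* × *d*. With an assumed *d* of 0.5, the shift is 0 if *f* = 0, 0.25 if *f* = 0.5 and 0.5 if *f* = 1. The documents give neither *f* nor *d*, nor the sign of *d*. The table only converts assumptions and estimates nothing about this trial.

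**The case against.** The best case on the other side has four parts.

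- **Some first-visit data may come first in practice.** Stratification uses demographics that are verified as needed at the first visit, and section IV.D joins eligibility with baseline. This is plausible, but it does not settle the order for weights or questionnaires.
- **The incentive to distort is weak.** Both arms get the same yearlong programme and differ by one pre-session of 60-90 minutes. The remote weight is a photo from a study-provided scale, not a verbal report, and remote visits are a COVID-19 contingency of unstated frequency. This stands, and it is why the priority is no higher.
- **There are safeguards.** Weighing is arranged for all randomised people, the assessment is paid, and each coach delivers one class per arm under observation. The observation, however, is aimed at class delivery and not at baseline data.
- **The mediator analyses tolerate some imbalance.** They are labelled exploratory under Sample size and power. The Hypothesis 2.1 model has a baseline arm-difference term, and Hypothesis 2.2 adjusts for baseline scores. These would show or adjust for an imbalance without removing its cause.

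Three stronger readings are tempting and not supported. A reader might infer that the primary result will be biased, or put an inflated error rate on it. Any such rate would only restate an assumed shift. A reader might infer that sections IV.C and IV.D contradict each other, but IV.D lists visits and is silent on randomisation. A reader might infer that missing weights are ignored, but imputation is foreseen. What is absent is a rule for a missing baseline.

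**Conclusion.** The point holds as an avoidable weakness in procedure. The stated order puts randomisation before baseline assessment, and nothing withholds allocation in between. Questionnaires and remote baseline weights can therefore be collected with the arm known; the documents do not say that they will be.

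The size and direction of any effect cannot be derived. The effect on the weight contrast is near zero for in-person weights taken at the same visit, and otherwise depends on the two unknowns *f* and *d*. The consequence for the mediators is limited by their exploratory status. No sample-size or power figure changes. Priority is minor to moderate: the reason to act is that the primary outcome's reference value can be protected cheaply.

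This rests on reading the Recruitment list as a true sequence. If practice already puts baseline first, the change is mainly a clarification.

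**What to change.** Amend the Recruitment sequence in IV.C so that, after consent, the questionnaires are completed and the baseline weight is recorded before the REDCap assignment is made or released to participants and coaches. For remote visits, recorded means that the scale photo has been received. Required fields ahead of the Randomization Module can enforce this. State who discloses the allocation and when. Section IV.D needs no correction, though a cross-reference would help.

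Making the assignment only at that point is cleaner than making it earlier and withholding it, because the second option leaves people who never send a photo randomised with no baseline weight.

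For anyone already randomised under the current order, report by arm the timing of baseline relative to randomisation, the weighing mode (in person or remote) and the number with no baseline weight.

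**Cost.** A short amendment and a field rule, with no added visit and no change in sample size; a reminder contact for remote photos may be needed. Remote participants are allocated up to 1-2 weeks later. The binding deadline is the pre-session, held 1-2 weeks before classes start, so a remote first visit would need to fall about 2-4 weeks before classes (1 + 1 to 2 + 2). People who never send a photo are lost before randomisation, which matters in a pragmatic trial of an underserved population. The documents do not indicate how many that would be, so the number should be reported.

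The change protects baseline only. A 12-month weight sent from home is collected with the arm known under either order.
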